1.2. Schema

Figure 1 Schematic Overview of the Study

* Participants will be retreated with JNJ-77242113 after a loss of $\geq 50\%$ PASI improvement observed at Week 24.

4525_v8

DBL=database lock; PE=primary endpoint; Q12w=every 12 weeks; R=randomization; SE=secondary endpoint; SFU=safety follow-up visit.

1.3. Schedule of Activities (SoA)

1.3.1. Schedule of Activities – Screening Through Week 52

Period	Screen-ing	Placebo-controlled					JNJ-77242113 Treatment		Randomized withdrawal and retreatment						Unsch-eduled ^{a,b}	Notes: See Section 1.3.2 for Early Termination Visit procedures.
Week (W)	-5-0	0	2	4	8	12	16	20	24	28	32	36	44	52		
Visit Window (days)			±2	±2	±4	±4	±4	±4	±4	±4	±4	±4	±4	±4		
Study Procedure																
Screening/Administrative																
ICF/assent	X															Must be signed before first study-related activity.
ICF/assent for optional skin biomarker substudy	X															ICF/assent for optional substudies can be signed at the Week 0 visit before any related substudy assessment are performed.
ICF/assent for optional photography substudy	X															
ICF/assent for optional DNA/genomics substudy	X															
Demographics	X															
Medical history	X															Including psoriasis diagnosis.
Prestudy therapy	X															Review of medications, including previous psoriasis medications.
Inclusion/exclusion criteria (Section 5)	X	X														Minimum criteria for the availability of documentation supporting the eligibility criteria are described in Source Documents section of Appendix 2 . Check clinical status again before first dose of study intervention.
Chest imaging	X															Chest radiographs or CT ≤12 weeks before first administration of study

Period	Screen-ing	Placebo-controlled					JNJ-77242113 Treatment		Randomized withdrawal and retreatment						Unsch-eduled ^{a,b}	Notes: See Section 1.3.2 for Early Termination Visit procedures.
Week (W)	-5-0	0	2	4	8	12	16	20	24	28	32	36	44	52		
Visit Window (days)			±2	±2	±4	±4	±4	±4	±4	±4	±4	±4	±4	±4		
Study Procedure																
																intervention. This is optional for adolescent participants.
IGRA	X															Includes either QuantiFERON®-TB Gold Plus or T-SPOT® TB. In addition to IGRA, tuberculin skin test may be used to screen for latent TB if preferred by local health authorities or the investigator.
Hepatitis B and C serology	X															
HIV antibody test	X															
FSH	X															If needed to confirm postmenopausal status.
eDiary Compliance	X	X	X	X	X	X	X									Check eDiary completion and retraining of participants as necessary. Additional checks maybe performed as needed.
Study Intervention Administration																
Randomization		X							X							Randomization at W24 is rerandomization for adult participants receiving JNJ-77242113 from W0 to W24.
Dispense study intervention		X	X	X	X	X	X	X	X	X	X	X	X	X		Dispense study intervention after all other procedures. Study intervention may also be dispensed between visits.
Administer study intervention		Oral study intervention will be self-administered daily (Section 6.1).														Study intervention will be taken at the site during the baseline (W0), W4, and W16 visits, where both a pre- and post-dose PK sample will be drawn. At W16 study intervention will be

Period	Screening	Placebo-controlled					JNJ-77242113 Treatment		Randomized withdrawal and retreatment						Unscheduled ^{a,b}	Notes: See Section 1.3.2 for Early Termination Visit procedures.
Week (W)	-5-0	0	2	4	8	12	16	20	24	28	32	36	44	52		
Visit Window (days)			±2	±2	±4	±4	±4	±4	±4	±4	±4	±4	±4	±4		
Study Procedure																
																taken from a newly dispensed drug blister pack at the visit.
Study intervention accountability			X	X	X	X	X	X	X	X	X	X	X	X	X	
Efficacy Assessments																
PROs: Complete in the order shown before any tests, procedures, or consultations for all visits unless otherwise noted.																
PSSD (24-hour recall)	Daily Diary beginning at Screening through W16.															
PSSD (7-day recall)							X	X	X	X	X	X	X	X	X	
DLQI or CDLQI		X	X	X	X	X	X	X	X	X	X	X	X	X	X	
GenPs-SFQ		X			X		X		X			X		X		W8-W52: Collect only for participants with active genital psoriasis at W0. Only for participants ≥18 years of age.
PROMIS-29 or PROMIS-25		X			X		X		X			X		X		PROMIS-25 is only for participants <18 years of age.
TSQM-E							X							X		Effectiveness domain only (Section 8.2.10.7).
EQ-5D-5L		X			X		X		X			X		X		
PsA Pain Assessment		X			X		X							X		W8-W52: Collect only for participants with a diagnosis of PsA at or before screening.
PsA Disease Activity Assessment		X			X		X							X		
Acceptability and palatability assessment		X					X									Only for participants <18 years of age.
ClinROs																
IGA	X	X	X	X	X	X	X	X	X	X	X	X	X	X	X	
PASI	X	X	X	X	X	X	X	X	X	X	X	X	X	X	X	
BSA	X	X	X	X	X	X	X	X	X	X	X	X	X	X		

Period	Screening	Placebo-controlled					JNJ-77242113 Treatment		Randomized withdrawal and retreatment						Unscheduled ^{a,b}	Notes: See Section 1.3.2 for Early Termination Visit procedures.
Week (W)	-5-0	0	2	4	8	12	16	20	24	28	32	36	44	52		
Visit Window (days)			±2	±2	±4	±4	±4	±4	±4	±4	±4	±4	±4	±4		
Study Procedure																
ss-IGA		X			X		X		X			X		X		W8-W52: collect only for participants with active scalp psoriasis at W0.
sPGA-G		X			X		X		X			X		X		W8-W52: collect only for participants with active genital psoriasis at W0.
hf-PGA		X			X		X		X			X		X		W8-W52: collect only for participants with active palmoplantar psoriasis at W0.
f-PGA		X			X		X		X			X		X		W8-W52: collect only for participants with active nail psoriasis at W0.
mNAPSI		X			X		X		X			X		X		
PGA of Disease Activity		X			X		X							X		Only for participants <18 years of age with a previous diagnosis of PsA at or before screening.
Photography (optional substudy)		X		X			X									
Safety Assessments																
Full physical examination	X	X												X		
Targeted physical examination			X	X	X	X	X	X	X	X	X	X	X			Recommended to include skin and general exam with additional organ systems based on investigator's judgement.
Tanner Staging		X												X		W52: Only for participants <18 years old at screening with previous Tanner stage <5.
Height	X	X					X							X		At screening, W16 and W52: Only for participants <18 years at Screening.
Weight	X	X					X							X		At screening: Only for participants <18 years of age.

Period	Screen-ing	Placebo-controlled					JNJ-77242113 Treatment		Randomized withdrawal and retreatment						Unsch-eduled ^{a,b}	Notes: See Section 1.3.2 for Early Termination Visit procedures.
Week (W)	-5-0	0	2	4	8	12	16	20	24	28	32	36	44	52		
Visit Window (days)			±2	±2	±4	±4	±4	±4	±4	±4	±4	±4	±4	±4		
Study Procedure																
Vital signs	X	X	X	X	X	X	X	X	X	X	X	X	X	X	X	Including temperature, heart rate, respiratory rate, and blood pressure.
12-lead triplicate ECG	X						X							X		
PHQ-9	X	X	X	X	X	X	X	X	X	X	X	X	X	X		
C-SSRS	X	X	X	X	X	X	X	X	X	X	X	X	X	X		
TB evaluation	X	X	X	X	X	X	X	X	X	X	X	X	X	X	X	
Pregnancy test for female participants of childbearing potential	X (serum)	X	X	X	X	X	X	X	X	X	X	X	X	X		A negative urine test result is required at each visit prior to dispensing study intervention. A urine pregnancy test may be performed at any time during the visit including before PROs.
Clinical Laboratory Tests																
Hematology	X	X		X	X	X	X	X	X	X	X	X	X	X		
Chemistry	X	X		X	X	X	X	X	X	X	X	X	X	X		
Lipid panel		X					X							X		Fasting requirement: ≥6 h unless medically contraindicated.
hs-CRP		X					X							X		
Urinalysis		X		X	X	X	X	X	X	X	X	X	X	X		May be performed any time during the study visit including before PRO collection.
Clinical Pharmacology Assessments																
JNJ-77242113 concentration (plasma) ^c		X		X		X	X			X		X		X		Collect 1 trough and 1 peak sample at W4 and W16. Details to be specified during training. If peak/trough collection at the W4 and W16 visits is not feasible, collection at an alternative visit is allowed.

Period	Screen-ing	Placebo-controlled					JNJ-77242113 Treatment		Randomized withdrawal and retreatment						Unscheduled ^{a,b}	Notes: See Section 1.3.2 for Early Termination Visit procedures.
Week (W)	-5-0	0	2	4	8	12	16	20	24	28	32	36	44	52		
Visit Window (days)			±2	±2	±4	±4	±4	±4	±4	±4	±4	±4	±4	±4		
Study Procedure																
Antibodies to JNJ-77242113 (serum)		X		X		X	X			X		X		X		
Pharmacodynamics and Biomarkers																
Serum Biomarkers	X	X		X			X		X	X		X		X		Sample collection and testing will comply with local regulations.
Skin biopsy (optional skin biomarker substudy)		X							X					X		W0: Collect 1 lesional and 1 nonlesional biopsy. W24 and W52: Collect 1 lesional biopsy. Sample collection and testing will comply with local regulations.
Pharmacogenomics (DNA)																
Whole blood sample collection (optional substudy)		X														May be collected after W0 without constituting a protocol deviation. Sample collection and testing will comply with local regulations.
Ongoing Participant Review																
Concomitant therapy	X	X	X	X	X	X	X	X	X	X	X	X	X	X	X	Record all medications taken and new or worsening AEs reported after signing the ICF.
Adverse events	X	X	X	X	X	X	X	X	X	X	X	X	X	X	X	

- Additional assessments may be performed at the Unscheduled Visit at the investigator's discretion.
- During the randomized withdrawal and retreatment period (Week 24 to Week 52) if a participant's psoriasis worsens and the participant and investigator would like to have the participant return to the site for reevaluation of PASI score an Unscheduled Visit can be conducted. At this visit if the participant is part of the blinded treatment group withdrawn from JNJ-77242113 treatment and has lost 50% or greater of their PASI score from Week 24, the participant will be retreated with JNJ-77242113 in a blinded manner. If a participant is not part of the withdrawn treatment group, they will continue on their treatment per study design.
- At Week 0, all blood samples should be collected prior to study intervention administration and the date and time of collection should be recorded as instructed in the laboratory manual. At all other study visits where applicable, the date and time of the dose prior to the PK sample should be recorded as instructed in the CRF completion guidelines.

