8. STUDY ASSESSMENTS AND PROCEDURES

Overview

The SoA summarizes the frequency and timing of efficacy, PK, immunogenicity, biomarker, pharmacogenomic, photography and safety measurements applicable to this study (Section 1.3).

All visit-specific PRO assessments must be conducted/completed before any tests, procedures, or other consultations to prevent influencing participant responses unless otherwise specified in the SoA. Refer to the PRO completion guidelines for instructions on the administration of PROs.

Prior to the first assessment, each participant will be provided with an electronic device to enter study-related data. Study-site personnel will train the participants on how to use the electronic device, including instructions to capture the data according to the study design and not to wait until the study-site visit to record information. Participants will be provided with written instructions on how to get 24-hour technical support, if needed, for operation of the electronic device.

ECGs should precede vital signs and both procedures should be completed prior to any invasive procedures. Vital signs should be recorded from the opposite arm from which blood samples are being taken.

Blood collections for PK and biomarker assessments should be kept as close to the specified time as possible. Other measurements may be done earlier than specified timepoints if needed. Actual dates and times of assessments will be recorded in the source documentation and according to the CRF guidelines and laboratory manual.

Blood Sample Collection

The total blood volume to be collected from each participant through the duration of the study will be approximately 300 mL (this total includes the optional blood sampling). Repeat or unscheduled samples may be collected for safety reasons or for technical issues with the samples.

Sample Collection and Handling

The actual dates and times of sample collection must be recorded in the CRF or laboratory requisition form. Refer to the SoA for the timing and frequency of all sample collections (Section 1.3).

Instructions for the collection, handling, storage, and shipment of samples are found in the laboratory manual that will be provided.

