#### **4.4.2.19. Analysis Related to Acceptability and Palatability (Adolescent) Through Week 16**

- The acceptability and palatability (e.g. sweetness, bitterness, overall, and swallowability) will be summarized at Week 0 and Week 16 by treatment among adolescent participants.

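### As scheduled, adolescents rate the tablet's taste and swallowability at Week 0 before they have taken one, so the Week 0 summary carries no information; Week 16 is sound

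*Protocol*

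**What the plan says.** The form has its own row among the PROs in Protocol 1.3.1, marked at Week 0 and Week 16. The only note on the row limits it to participants under 18. The rule at the head of the block is "PROs: Complete in the order shown before any tests, procedures, or consultations for all visits unless otherwise noted". Protocol section 8 repeats it as a requirement and gives the reason: "All visit-specific PRO assessments must be conducted/completed before any tests, procedures, or other consultations to prevent influencing participant responses". Section 8 allows exceptions only where the Schedule of Activities specifies them.

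The drug rows of the same schedule say "Dispense study intervention after all other procedures" and "Study intervention will be taken at the site during the baseline (W0), W4, and W16 visits". The Week 16 dose is "taken from a newly dispensed drug blister pack at the visit".

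Protocol 8.2.10.11 says that the questions concern the study drug. SAP 4.4.2.19 names sweetness, bitterness, an overall item and swallowability as examples, and states that the results "will be summarized at Week 0 and Week 16 by treatment among adolescent participants". SAP Appendix 2 (6.2) also lists acceptability and palatability among the PROs summarised at baseline.

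**The concern.** A rating of taste or swallowability means something only after the tablet has been in the mouth. The general PRO-first rule suits a questionnaire on symptoms or quality of life, where the visit itself could colour the answers. Applied to this form at Week 0, it places the question before the thing being asked about.

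At stake is half of the palatability data that this study plans to collect in adolescents. Protocol 6.1 lets those who have difficulty swallowing disperse the tablet in water, so first-dose taste and swallowability are real questions. A Week 0 table by treatment, filled with answers given before any exposure, would look like data and could be read as a comparison of the active and placebo tablets at first use.

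**Working it through.** The plan states no figure for this point beyond the number of adolescents, so the check follows the order of events and then counts forms.

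**Order of events at Week 0**

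1. The form is a PRO, so by the block rule and section 8 it comes before tests and procedures.
2. Exceptions must appear in the schedule. The pregnancy test and urinalysis rows do carry one, each allowing the test before the PROs. The acceptability row carries none.
3. Study drug is dispensed after the other procedures, and the first dose is taken on site at that visit.
4. No earlier exposure can inform the answer, because exclusion criterion 9 (Protocol 5.2) bars previous use of JNJ-77242113.

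The Week 0 form therefore precedes the first tablet.

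**Order of events at Week 16**

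1. The same rule places the form before the on-site dose.
2. The last tablets taken are then those of the arm assigned at Week 0.
3. Placebo participants receive JNJ-77242113 from Week 16 (Protocol 6.1, study arms), starting with the new pack. That dose comes after the form.

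The Week 16 summary by treatment is therefore correctly labelled.

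**Counts**

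- Allocation is 2:1. For the whole trial, 600 × 2/3 = 400 and 600 × 1/3 = 200, which matches Protocol 9.5.
- About 60 adolescents are planned (Protocol 4.1): 60 × 2/3 = 40 active and 60 × 1/3 = 20 placebo.
- Planned forms: 60 × 2 visits = 120. Week 0 share: 60/120 = one half.

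The table compares the schedule as written with two alternatives, to test the fix. It assumes that every adolescent completes both forms.

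| Timing relative to the on-site dose | Week 0 forms with no tablet taken | Week 16 placebo-arm forms completed after an active tablet |
|---|---|---|
| Before at both visits (as written) | 60 | 0 |
| After at both visits | 0 | 20 |
| After at Week 0, before at Week 16 | 0 | 0 |

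The first row is the plan. The second is not in the plan; it shows why one uniform move would be the wrong repair. The third leaves both summaries usable.

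**The case against.** The best counter-argument is that the written sequence is not meant to be absolute. At Week 16 the dose comes from a pack dispensed at that visit and a post-dose PK sample follows, so dispensing cannot literally be last. The stated purpose of putting PROs first, to avoid influencing answers, has little force for a question about the tablet. On-site dosing is scheduled at both visits where the form is given, so completion after the dose at Week 0 may well have been intended. The form and the PRO completion guidelines are not in these documents and may say so. The baseline listing in SAP Appendix 2 does not settle it either, because SAP 4.1 lets an efficacy baseline fall on the first dosing date.

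This shows that post-dose completion is a plausible intention. It does not remove the explicit PRO-first rule, from which other rows are expressly exempted and this one is not. A guideline that set a different time would contradict the protocol, and the two would still need reconciling.

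A reader might also infer that Week 16 is broken, with about 20 placebo-arm forms rating the active tablet. The documents do not support that. As written, the form precedes the crossover dose, and no passage tells sites to move it. The count of 20 arises only if someone moves the form after the dose at both visits. Even then, the unseen wording decides whether the answers would concern that day's tablet or the preceding weeks.

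The objection on materiality stands. Acceptability is not named as an endpoint in Protocol section 3 or SAP 1.1. If every Week 0 form were lost, Week 16 would still supply about 40 active and 20 placebo ratings after 16 weeks of use.

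**Conclusion.** The point holds for Week 0 only. Under the rules as written, about 60 of 60 Week 0 forms would be completed before any tablet is taken, and the Week 0 part of SAP 4.4.2.19 would be uninformative in both arms. The Week 16 part is valid and correctly labelled. It would be wrong to conclude that the plan forces a choice between one summary and the other, because a visit-specific order serves both.

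The size is minor: one descriptive summary in about 60 adolescents. Type I error, power, and the primary and key secondary analyses are untouched. The conclusion assumes that sites follow the schedule literally, that about 60 adolescents are enrolled at 2:1, and that no document outside those supplied sets another time for the form.

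**What to change.** By amendment, add a timing note to the acceptability and palatability row in Protocol 1.3.1:

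- **Week 0:** complete after the first on-site dose.
- **Week 16:** complete before the on-site dose from the newly dispensed pack, with reference to the tablets taken in Weeks 0 to 16. The form should not move after the dose here, since placebo adolescents would then have taken an active tablet first.

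In SAP 4.4.2.19, add that Week 0 forms completed before the first dose are set to missing. Protocol section 8 already requires actual dates and times of assessments to be recorded, so such forms should be identifiable.

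A protocol clarification communication is not the right vehicle. Protocol 10.2.1 limits it to wording that leaves study conduct unchanged, and moving the Week 0 form changes conduct.

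The cost is one schedule note and one SAP sentence. No assessment is added; adolescents complete one short form after the Week 0 dose instead of before it.

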4. STUDY DESIGN

4.1. Overall Design

This is a Phase 3 randomized, double-blind, placebo-controlled, parallel-group, multicenter interventional study with randomized withdrawal and retreatment in participants with moderate to severe plaque psoriasis.

A target of 600 participants will be enrolled in this study. Approximately 540 adults and 60 adolescent participants will be randomized with a 2:1 randomization ratio to JNJ-77242113 200 mg or placebo. Randomization will be separately performed for adult and adolescent groups. Within the adult group, randomization will be further stratified by baseline weight category (≤ 90 kg, >90 kg) and geographic region. Within the adolescent group, randomization will be further stratified by geographic region.

- Adult participants
 - JNJ-77242113 200 mg once daily
 - Week 0 to Week 24: Participants will be treated with JNJ-77242113 200 mg once daily
 - Week 24 to Week 52:
 - Participants who are PASI 75 responders or IGA 0 or 1 responders (ie, those who achieve an IGA score of 0 or 1 and have ≥ 2 -grade improvement from baseline) at Week 24 will be re-randomized 1:1 to either continue JNJ-77242113 or to be transitioned to placebo. Participants transitioned to placebo will be retreated with JNJ-77242113 200 mg once daily upon loss of $\geq 50\%$ of Week 24 PASI improvement or starting at Week 52 if loss of response is not observed. All participants will be treated with JNJ-77242113 at Week 52.
 - Participants who are both PASI 75 non-responders and IGA 0 or 1 non-responders at Week 24 will continue to receive JNJ-77242113 200 mg once daily through Week 52.

- Week 52 to Week 156: Participants will receive JNJ-77242113 200 mg once daily through Week 156.
- Placebo to JNJ-77242113 200 mg once daily
 - Week 0 to Week 16: Participants will receive placebo once daily through Week 16.
 - Week 16 to Week 156: Participants will cross-over to receive JNJ-77242113 200 mg once daily through Week 156.
- Adolescent participants
 - JNJ-77242113 200 mg once daily
 - Week 0 to Week 156: Participants will be treated with JNJ-77242113 200 mg once daily
 - Adolescents will not participate in re-randomization regardless of their PASI score or IGA score at Week 24.
 - Placebo to JNJ-77242113 200 mg once daily
 - Week 0 to Week 16: Participants will receive placebo once daily through Week 16.
 - Week 16 to Week 156: Participants will cross-over to receive JNJ-77242113 200 mg once daily through Week 156.

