Arm Description	
Adult participants will receive:
 
 - JNJ-77242113 200 mg QD through Week 24 - At Week 24: 
 o Participants who are both PASI 75 non-responders and IGA 0 or 1 non-responders at Week 24 will continue to receive JNJ-77242113 200 mg once daily through Week 52. o Participants who are PASI 75 responders or IGA 0 or 1 responders (ie, those who achieve an IGA score of 0 or 1 and have ≥ 2-grade improvement from baseline) at Week 24 will be re-randomized to receive either: 
 ▪ JNJ-77242113 200 mg once daily OR ▪ placebo (and will be retreated with JNJ-77242113 200 mg once daily upon loss of $\geq 50\%$ of their Week 24 PASI improvement) - At Week 52: 
 o All participants will receive JNJ-77242113 200 mg once daily through Week 156 
Adolescent participants will receive:
 
 - JNJ-77242113 200 mg once daily through Week 156 	
Adult and adolescent participants will receive:
 
 - Matching placebo for JNJ-77242113 on Week 0 through Week 16 - JNJ-77242113 200 mg once daily from Week 16 through Week 156
Associated Intervention Labels	Labels will be identical to maintain the blind.	Labels will be identical to maintain the blind.

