8.2.2. Psoriasis Area and Severity Index

The PASI is a system used for assessing and grading the severity of psoriatic lesions and their response to therapy ([Appendix 9](#)) ([Fredriksson 1978](#)). In the PASI system, the body is divided into 4 regions: the head, trunk, upper extremities, and lower extremities. Each of these areas is assessed and scored separately for erythema, induration, and scaling, which are each rated on a scale of 0 to 4 and extent of involvement on a scale of 0 to 6. The PASI produces a numeric score that can range from 0 to 72. A higher score indicates more severe disease.

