##### **4.3.1.1.2. Psoriasis Area and Severity Index (PASI)**

Refer to section 4.2.1.1 for details.

Meeting PASI 75 criteria: defined as having  $\geq 75\%$  improvement in PASI from baseline.

Meeting PASI 100 criteria: defined as having 100% improvement in PASI from baseline.

The time to loss of PASI 75 response through Week 52: PASI 75 response will be assessed at each visit between Week 24 and Week 52. Participants who experience a loss of PASI 75 response ( $< 75\%$  improvement from baseline) at any visit between Week 24 and Week 52 will be considered as having an 'event'. The time to loss of PASI 75 response is defined as the time from rerandomization at Week 24 to the visit of loss of PASI 75 response. Participants who do not experience any event between Week 24 and Week 52 will be censored at the last disease assessment visit or Week 52.

The time to loss of PASI 90 response through Week 52: similar to the definition of time to loss of PASI 75 response except using loss of PASI 90 response, which is when  $< 90\%$  improvement from baseline is observed.

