**ICEs and their corresponding strategies:**

Same ICEs 1-3 as those defined in the co-primary estimands. In addition, ICE 4 is defined as meeting criteria of loss of  $\geq 50\%$  Week 24 PASI improvement. Patients with this ICE will be handled using the composite strategy.

**Variable, Population and Population Level Summary:** Refer to [Table 4](#)

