##### From Week 24 Through Week 52 – Randomized Withdrawal and Retreatment Period

###### Randomized Withdrawal period

- The Life table method will be used to estimate the distribution of time to loss of  $\geq 50\%$  of the Week 24 PASI improvement (i.e., time to retreatment) after withdrawal. The median time to loss of  $\geq 50\%$  of the Week 24 PASI improvement will be provided.
- The proportion of PASI responses (PASI 75, 90, and 100) will be summarized over time from Week 24 through Week 52 for participants randomized at Week 24.
- The change and percent change from baseline in PASI total score will be summarized over time from Week 24 through Week 52 for participants randomized at Week 24.

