##### **Summary through Week 52 and /or through the reporting period (approximately the date when last participant finishing Week 52 visit):**

Safety data will be summarized by intervention group defined as follows:

- Placebo → JNJ-77242113: all participants who were randomized to placebo at Week 0, and later crossed over to receive treatment with JNJ-77242113 at or after Week 16. Only the safety events/measurements from these participants that occurred at or after Week 16 will be included.
- JNJ-77242113: Participants who were randomized to JNJ-77242113 at Week 0 and were treated with JNJ-77242113. All the safety events/measurements from these participants that occurred at or after Week 0 administration will be included in this group. However, safety events that occurred during the withdrawal period (on and after Week 28 and before retreatment) may be excluded for participants who were rerandomized to placebo at Week 24.
- Combined JNJ-77242113: all participant as described above in the Placebo → JNJ-77242113 and the JNJ-77242113 groups.

In addition, selected safety analysis from Week 24 through Week 52 may be performed among participants who were randomized to either receive placebo or continue to receive JNJ-77242113 at Week 24.

- Placebo (withdrawal): Participants who were randomized to JNJ-77242113 at Week 0, were PASI 75 or IGA 0 or 1 responders at Week 24, and rerandomized to placebo group at Week 24. Only the safety events/measurements from these participants that occurred at or after Week 24 randomization and before retreatment with JNJ-77242113 will be included in this group.
- Placebo → retreatment: Participants who were randomized to placebo at Week 24, started treatment with placebo, and retreated with JNJ-77242113 upon loss of 50% Week 24 PASI improvement. Only the safety events that occurred at or after their first retreatment of JNJ-77242113 will be included in this group.
- Placebo (combined 1 and 2 above): Participants who were randomized to placebo at Week 24. All safety events/measurements from these participants that occurred at or after Week 24 randomization will be included.
- JNJ-77242113 (Rerandomization): Participants who were randomized to JNJ-77242113 at Week 24 and continue to receive treatment with JNJ-77242113. All safety events occurred at or after Week 24 rerandomization will be included in this group.

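### Footnote b of the Schedule of Activities misstates the Unscheduled Visit retreatment trigger as a loss of PASI score instead of a loss of PASI improvement

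*Protocol*

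**What the plan says.** Footnote b of Protocol 1.3.1 allows an Unscheduled Visit when psoriasis worsens in the randomized withdrawal and retreatment period. If a participant in the withdrawn group "has lost 50% or greater of their PASI score from Week 24, the participant will be retreated with JNJ-77242113 in a blinded manner".

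The other statements of the trigger are built on improvement, not score:

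- Protocol 4.1: retreatment on loss of at least 50% "of Week 24 PASI improvement or starting at Week 52 if loss of response is not observed".
- Protocol 6.1, arm description: loss of at least 50% "of their Week 24 PASI improvement". The synopsis, the schema note in 1.2 and the ethics discussion in 4.2.2 agree.
- SAP 4.3.1.2.1, for the Week 52 estimands: "In addition, ICE 4 is defined as meeting criteria of loss of" at least 50% of the Week 24 PASI improvement.
- SAP 4.4.2.5: the time-to-event summary is for loss of at least 50% "of the Week 24 PASI improvement (i.e., time to retreatment) after withdrawal".
- SAP 4.5, safety group: participants "retreated with JNJ-77242113 upon loss of 50% Week 24 PASI improvement". SAP 1.2 and the retreatment analysis in SAP 4.4.2.2 use the same basis.

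Protocol 8.2.2 fixes the direction of the scale: "A higher score indicates more severe disease".

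**The concern.** Footnote b is the only text that names the Unscheduled Visit as a point of retreatment. From Week 36 the scheduled visits are eight weeks apart (36, 44, 52), so that visit is where a relapse between visits would be picked up. A threshold stated on the wrong quantity there is an error in an instruction that decides who gets active drug.

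Two things could go wrong if it were followed:

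- **Literal reading.** A participant who relapses would not meet the trigger. Protocol 4.2.2 relies on retreatment as the safeguard for those withdrawn to placebo, so that safeguard would fail at this visit.
- **Reading as a 50% rise in score.** A participant could be put back on active drug while still a PASI 75 responder, well before the rule on which the SAP's retreatment analyses are built.

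**Working it through.** **The plan's own figures for this period.** Protocol 9.5 assumes 540 adults, 2:1 allocation and 75% PASI 75 responders, re-randomized 1:1: 540 × 2/3 × 0.75 / 2 = 135 per group. A pooled-variance normal approximation at two-sided 0.05 gives 95.2%, 97.0% and 98.7% for 60% v 80%, 65% v 85% and 70% v 90%. The plan states 95.2%, 97.0% and 98.6%. These figures do not depend on the trigger wording.

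**Inputs.** Let B be baseline PASI and W the Week 24 PASI. Entry requires B of at least 12 (Protocol 5.1). The value B = 20 and the individual W values are assumptions for illustration.

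**Formulas.**

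- Improvement rule: retreat at PASI ≥ W + 0.5(B − W).
- Footnote, literal: PASI ≤ 0.5W.
- Footnote, as a 50% rise: PASI ≥ 1.5W.

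The percentage in brackets is the improvement from baseline remaining at the trigger.

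| B | W | Improvement rule | Literal footnote | 50% rise |
|---|---|---|---|---|
| 12 | 3 | ≥ 7.5 (37.5%) | ≤ 1.5 | ≥ 4.5 (62.5%) |
| 20 | 5 | ≥ 12.5 (37.5%) | ≤ 2.5 | ≥ 7.5 (62.5%) |
| 20 | 2 | ≥ 11 (45%) | ≤ 1 | ≥ 3 (85%) |
| 20 | 1 | ≥ 10.5 (47.5%) | ≤ 0.5 | ≥ 1.5 (92.5%) |
| 20 | 0 | ≥ 10 (50%) | ≤ 0 | ≥ 0 |

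**What follows.**

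1. The literal trigger moves in the direction of improvement and contradicts the footnote's own condition that psoriasis has worsened.
2. The gap between the improvement rule and a 50% rise is W + 0.5(B − W) − 1.5W = 0.5B − W. A PASI 75 responder has W ≤ B/4, so the gap is at least B/4: 3.0 points at B = 12 and 5.0 at B = 20.
3. At W = 0 both readings of the footnote are met with no change in PASI, so neither gives a usable threshold.
4. If I is the proportional improvement at Week 24, the improvement remaining at a 50% rise is 1 − 1.5(1 − I). It is still at least 75% only if I ≥ 1 − 0.25/1.5 = 83.3%, and at least 90% only if I ≥ 1 − 0.10/1.5 = 93.3%. So the participant with B = 20 and W = 2 would be retreated while holding PASI 75, but after losing PASI 90.

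**Link to the Week 52 analysis.** Under SAP 4.3.1.2.1, ICE 4 is the loss of improvement itself. A participant retreated at PASI 3 in the W = 2 example would not meet it, and the Week 52 score on active drug would be used as observed. Protocol 9.3.3 instead describes ICE 4 as meeting the retreatment criterion. On that wording, anyone retreated under the footnote would arguably count as a Week 52 non-responder. The two descriptions coincide only if the retreatment criterion is the improvement rule.

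**The case against.** The strongest reply is that this is a slip of one word with an obvious intent. Much of that stands. Protocol 4.1 and 6.1 state the rule without tying it to a type of visit, so it already covers unscheduled visits; footnote b is not the sole rule there. The footnote says lost, not risen, so the early-retreatment thresholds rest on a reading the text does not state. Sites are blinded (Protocol 6.4) and treatment is assigned centrally through the IWRS (Protocol 6.3). Dosing therefore changes only if that system or the visit instructions were built from the footnote, and SAP 4.4.2.5 points to the improvement rule as the operating one.

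A reader might go further and infer that the Week 52 withdrawal comparison is biased toward no difference. The documents do not support that. It needs three things together: the footnote taken as a 50% rise, the central system or instructions following it, and ICE 4 applied as in SAP 4.3.1.2.1 rather than as in Protocol 9.3.3. The documents establish neither of the first two, and they differ on the third.

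Nor should one infer that the time-to-loss endpoints are immune. SAP 4.3.1.1.2 counts a loss "at any visit between Week 24 and Week 52 will be considered as having an" event, but in the W = 2 example retreatment would come before any loss of PASI 75 and could prevent one.

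What the reply does not remove is that the one sentence written for this visit gives a wrong threshold for a dosing decision.

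**Conclusion.** The point holds as a minor error in an operative rule. The wording conflict is certain, and the footnote cannot sensibly be applied as written: it points the wrong way when read literally, comes at least B/4 PASI points too early for a Week 24 PASI 75 responder when read as a 50% rise, and gives no usable threshold at a Week 24 PASI of 0. The intended rule is not in doubt.

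The effect on conduct cannot be sized, because neither document says how the retreatment trigger is programmed or worded for sites, or how often it would be reached at an Unscheduled Visit. No change to power, sample size or type I error follows. The Week 16 co-primary endpoints are measured before this period and are unaffected.

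**What to change.** In footnote b, restate the trigger as having lost at least 50% "of their Week 24 PASI improvement", matching Protocol 6.1. Confirm once, against the assignment specification, that the central system applies that rule at both scheduled and unscheduled visits.

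The cost is one phrase and one check, with no change to the estimands, sample size or data collected. If the check shows that the system already uses the improvement rule, the clarification communication in Protocol 10.2.1 could carry the correction until the next amendment. No added sensitivity analysis is needed unless retreatment outside the improvement rule is found. Any such case would fit the existing wrong-treatment deviation category in SAP Appendix 3, and its handling at Week 52 should then be specified.
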